
Procedures to Avoid Withdrawal or Lost to Follow-Up
	
Avoiding Withdrawal of Consent or Lost to Follow-Up
 
As part of the informed consent process, only subjects who fully understand and agree to full participation and long-term follow-up should be consented to participate. It is important that subjects understand the long-term duration and purpose of a cardiovascular outcome trial and that the subject (or designee) continue to allow follow-up through global study completion which could be several years, even post subject’s permanent discontinuation of study medication.
 
In all cases of impending study medication discontinuation or subject request for stopping study visits, Investigators will discuss with the subject their options of continuing in the study. It is important to continue to follow subjects that discontinue study medication through global study completion at a frequency and approach that is agreed to between the Investigator and subject. Visit schedule and assessments are flexible and at the discretion of the Investigator and subject and will be clearly documented in the medical chart. Optimal data collection would include the following assessments through global study completion.
 
 • EOS subject status (must collect at minimum) • MACE Endpoint Questionnaire • AE Assessment 
Alternative options to support continued follow-up include but are not limited to the following:
 
 1. Reduced frequency of on-site visits 2. Telephone visits in lieu of on-site visits 3. Telephone or any contact method

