5.3 Secondary Efficacy Endpoints

The key secondary efficacy endpoints include the following:

- Mean change in Hb value between Baseline (mean pretreatment Hb) and the secondary evaluation period (Weeks 40-52)
- Proportion of subjects with Hb values within the target range during the primary evaluation period (Weeks 24-36)
- Proportion of subjects with Hb values within the target range during the secondary evaluation period (Weeks 40-52)

Other secondary efficacy endpoints include:

- Proportion of time with Hb values within the target range during the primary evaluation period (Weeks 24-36)
- Proportion of time with Hb values within the target range during the secondary evaluation period (Weeks 40-52)
- Proportion of subjects with Hb increase of >1.0 g/dL from Baseline

- Time to achieve Hb increase of >1.0 g/dL from Baseline
- Mean change in Hb between Baseline (mean pretreatment Hb) and the primary evaluation period (mean Hb from Weeks 24-36) stratified by pre-baseline ESA exposure
- Progression of CKD
- Proportion of subjects receiving IV iron therapy from Baseline visit to Week 52
- Mean monthly dose of IV elemental iron administered from Baseline to Week 52 in subjects who have received IV iron
- Proportion of subjects receiving RBC transfusion(s) from Baseline to Week 52
- ESA rescue
- Dose adjustments from Baseline to Week 52
-

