7.5.2 Subject Completion

A subject will be considered as having completed the study, regardless of whether they are on or off study medication (vadadustat or darbepoetin alfa), if the subject is followed until global study completion (end of trial). The table outlines the different categories of subjects and handling the global study completion activities.

Subject Status at time of Global Study Completion	End of Treatment (EOT)	End of Study (EOS)
Subject on study medication (includes those on temporary interruption)	After announcement of global study completion: 
 • Perform EOT visit • Perform the Follow-up visit 4 weeks after EOT visit and include End of Study (EOS) subject status 	Not applicable The EOS subject status will be captured as part of the Follow-up visit
Subject permanently discontinued study medication and continues to be followed in the study	At time of permanent discontinuation of study medication: 
 • Perform EOT visit • Perform the Follow-up visit 4 weeks after EOT visit 	Optimal data collection would include the following assessments: 
 • EOS subject status (must collect at minimum) • MACE Endpoint Questionnaire • AE Assessment
Subject Lost to Follow-up	Not applicable	Work with third party vendor to ascertain vital status and complete EOS subject status If subject-site contact is reestablished and possible, collect available information for EOS subject status
Subject Withdrawn Consent	Not applicable	Complete the EOS subject status form at time of withdrawal of consent, absolute refusal of ALL methods of MACE and health status follow-up

Subject Death	Not applicable	Complete the EOS subject status form at the time of death (see Section 10 Adverse Events for more details on other actions related to reporting a death)
---------------	----------------	--

The need for rescue therapy does not constitute study completion and is not a criterion for subject withdrawal from the study. Also, the occurrence of a safety endpoint, or if a subject progressed to chronic dialysis dependent CKD (DD-CKD), does not constitute study completion and is not a criterion for subject withdrawal from the study or study medication (vadadustat or darbepoetin alfa).

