If new elevations in ALT or AST > 3 times ULN, **without** an elevation of total serum bilirubin >2 times ULN are identified, the following steps are to be taken:

- Temporary discontinuation of Investigational Medicinal Product (IMP);
- Repeat testing of ALT, AST, ALP, and total bilirubin, should be completed within 48 to 72 hours to confirm the abnormalities and to determine trend;
- IMP should not be resumed until monitoring indicates abnormalities have resolved or have stabilized.

Details on the management of subjects with other ALT and AST abnormalities are further described in [Section 9.4, Study Medication Stopping Rules](#).

Worsening of Anemia – In this study, it is possible that some subjects may experience a worsening of anemia. As the primary endpoint of this study assesses Hb response, worsening of anemia is captured as part of this efficacy parameter. Worsening of anemia should not be considered an AE unless the worsening of anemia is associated with a cause *other than* the subject's CKD.

Transplantation – During this long-term study, it is anticipated that some subjects may receive a kidney transplant. These events will not be recorded as AEs. Subjects will discontinue study medication for receipt of a kidney, other solid organ, hematopoietic stem cell or bone marrow transplant and should continue with the Schedule of Activities and safety assessments as described in [Section 7.5.5.2, Permanent Discontinuation of Study Medication](#).

Malignancy – During this long-term study, some subjects may develop a newly diagnosed malignancy or a recurrence of a malignancy. At the discretion of the Investigator, these subjects may continue study medication (vadadustat or darbepoetin alfa). For reporting of adverse events of malignancy, see [Section 10.1.2 Serious Adverse Events](#).

Renal-Related Events - Some subjects will experience a progression of their CKD over the course of this study as part of the natural course of the disease. In addition, the study population is prone to experience acute, transient loss of kidney function of different etiologies, sometimes concomitantly complicated by progression of CKD.

To ensure consistent reporting of renal events, the following guidelines are to be used when reporting a renal-related AE:

- The following situations **should always be reported as SAEs** with seriousness criterion “medically important,” if no other seriousness criteria are met (see Section 10.1.2, Serious Adverse Events):

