Abbreviations: AE = adverse event; ALT/SGPT = alanine aminotransferase/serum glutamic-pyruvic transaminase; AST/SGOT = aspartate aminotransferase/serum glutamic oxaloacetic transaminase; BUN = blood urea nitrogen; CBC = complete blood count; CPK = creatine phosphokinase; CRF = case report form; diff = differential; ECG = electrocardiogram; eGFR = estimated glomerular filtration rate; EOT = end of treatment; ESA = erythropoiesis-stimulating agent; HDL = high density lipoprotein; Hb = hemoglobin; HIF = hypoxia inducible factor; ICF = informed consent form; I/E = inclusion/exclusion; INR = international normalized ratio; IWR = interactive web response; LDH = lactate dehydrogenase; LDL = low density lipoprotein; MACE = major adverse cardiovascular event; MCH = mean corpuscular hemoglobin; MCHC = mean corpuscular hemoglobin concentration; MCV = mean corpuscular volume; med = medication; PK = pharmacokinetic; PS = Pre-Screening; PT = prothrombin time; PTT = partial thromboplastin time; RBC = red blood cell; RDW = red cell distribution width; SV1 = Screening visit 1; SV2 = Screening visit 2; TIBC = total iron binding capacity; Trtmt = treatment; TSAT = transferrin saturation; uACR = urine albumin to creatinine ratio; VEGF = vascular endothelial growth factor; WBC = white blood cell; wks = weeks.

- [a] The Screening period is a maximum of 8 weeks in duration. The Baseline visit must be performed at a minimum of 4 days from the last Screening visit (SV2), or date of last re-test.
- [b] The Follow-up visit can be performed either in person OR via the telephone.
- [c] The EOT visit will be performed at the time a subject permanently discontinues study medication (vadadustat or darbepoetin alfa) or for subjects on study medication at the time of notification of global study completion. It is important to continue to follow subjects that discontinue study medication through global study completion at a frequency and approach that is agreed to between the Investigator and subject. Visit schedule and assessments are flexible and at the discretion of the investigator and subject and will be clearly documented in the medical chart.

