### *Study CI-0015*

- Conversion and Maintenance Period (Weeks 0-52):
  - Weeks 0 to 23: conversion to study treatment for maintaining Hb
  - Weeks 24 to 36: PEP
  - Weeks 40 to 52: SEP

After Week 52, subjects in both studies will proceed to the following 2 periods:

- **Long-Term Treatment Period (Weeks 53-End of Treatment [EOT]):** continued treatment with study medication to assess long-term safety
- **Follow-up Period (EOT + 4 weeks):** post-treatment visit (either in person or by telephone) to assess safety

The duration of the trial will depend on how long it takes for a total of 631 adjudicated MACE to occur in the 2 studies combined. A separate SAP will describe the planned MACE analyses, including the method planned for pooling data from the 2 PRO2TECT studies.

The safety reporting period for a subject enrolled in this study begins upon randomization and ends at the final protocol-required study contact (visit or telephone), also known as a subject's end of study (EOS). In addition, the Investigator should report any adverse event (AE) that occurs after this period if he or she assesses it as possibly or probably related to the study medication.

According to the schedule of visits in the protocol, no laboratory assessments, physical exams, or other procedures are planned after the subject's permanent discontinuation of study medication, also known as EOT; however, AE and rescue therapy assessments, including monitoring for MACE endpoints, will continue until a subject's EOS.

The analysis time periods for efficacy divide the Correction/Conversion and Maintenance periods, Year 1 collectively, into four windows (see [Table 1](#)).

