### 6.3.7 Endpoints Related to RBC Transfusion

These endpoints address RBC transfusion for the entire length of study, by the four analysis time periods in Year 1 (see [Section 5.1](#)), and in the long-term treatment/follow-up period (Week 52 to EOS) unless otherwise specified.

- Receipt of any RBC transfusion
- Time to first RBC transfusion (for entire study)
- Total number of RBC transfusion episodes received
- Rate of RBC transfusions, calculated as the number of episodes divided by the duration of at-risk follow-up in person-years

RBC transfusion may be considered rescue when “Worsening Anaemia due to CKD” is the reason indicated on the CRF.

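### The documents disagree on whether RBC transfusions are recorded after study drug is stopped, yet the SAP analyses them to end of study without tying follow-up to ascertainment

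*Protocol*

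**What the plan says.** **Analysis.** Protocol 5.3 lists "Proportion of subjects receiving RBC transfusion(s) from Baseline to Week 52" among the other secondary endpoints. SAP 6.3.7 has a wider window: "These endpoints address RBC transfusion for the entire length of study, by the four analysis time periods in Year 1", and also Week 52 to end of study (EOS). The endpoints are receipt of any transfusion, time to first transfusion, number of episodes, and "Rate of RBC transfusions, calculated as the number of episodes divided by the duration of at-risk follow-up in person-years". Receipt is compared by a stratified Mantel-Haenszel risk difference (SAP D.1). The count uses a zero-inflated Poisson model with offset LN_FUT (Exhibit D 2). Time to first transfusion uses Kaplan-Meier and Cox methods (D.3).

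**Collection off drug.** The Synopsis and Protocol 7.5.5.4 state that "Optimal data collection would include the following assessments through global study completion"; 7.5.2 and 9.3.12 repeat the list. It has three items: one marked "EOS subject status (must collect at minimum", then the MACE questionnaire and AE assessment. Appendix A note [c] adds: "Visit schedule and assessments are flexible and at the discretion of the investigator and subject". The last visits that explicitly list transfusions are EOT (9.3.9) and the Follow-up visit 4 weeks later (9.3.10).

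**Text pointing the other way.** Protocol 11.5 expects subjects who stop drug to keep to the planned visits and assessments. Protocol 8.5.3 says, with no time limit, that transfusions are documented. Note [dd] brings the Follow-up visit activities, which include transfusions, into the EOS assessment of off-drug subjects. SAP 2.2 states that "AE and rescue therapy assessments, including monitoring for MACE endpoints, will continue until" the subject's EOS.

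**The concern.** The analysis window runs to EOS, but a site that follows the three-item list has no reason to ask about transfusions once the Follow-up visit is over. A transfusion given later may never reach the database. The subject then counts as untransfused in the yes/no endpoint, and may go on contributing person-time and risk-set membership in the others. Absolute transfusion frequency would be too low in both arms. If subjects leave drug faster in one arm (lack of efficacy is a listed reason, Protocol 7.5.5), that arm has more unobserved time and could appear to need fewer transfusions.

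**Working it through.** **Step 1. Can another route recover the data?** Protocol 10.1.1 excludes procedures from AE reporting and adds: "Worsening of anemia should not be considered an AE unless the worsening of anemia is associated with a cause" other than CKD. Yet SAP 6.3.7 treats a transfusion as rescue when the recorded reason is worsening anaemia due to CKD. So AE assessment leaves out the transfusions of most interest. Concomitant medication does not settle it: Appendix A note [x] stops at EOT, while 9.2.1 continues to the final required visit.

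**Step 2. Where does transfusion follow-up end?** At-risk follow-up in SAP 6.3.7 and LN_FUT in Exhibit D 2 are not defined. SAP D.3 gives censoring rules only for laboratory endpoints and CKD progression. SAP 5.4 defaults to observed data without imputation. The MACE SAP (Sections 4 and 4.4) does have the rule that is missing here: it censors at the last contact at which all components were assessed.

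**Step 3. How large could the effect be?** The plan states no transfusion or stopping rate, so there is no figure to reproduce and this is an illustration. From the documents: 925 subjects per arm (SAP 2.6), T = 2 years of follow-up (MACE SAP 2.5.1), capture to EOT plus L = 4/52 = 0.0769 years. Assumed: a constant transfusion hazard λ, the same in both arms and on and off drug; exponential drug stopping at rate d; nothing captured after EOT + 4 weeks.

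Ascertained person-time is A(d) = L + [1 − exp(−d(T − L))]/d.

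| d per year | A(d), years | Unobserved share of 2 years | Rate ratio versus d = 0.20, all follow-up in denominator |
|---|---|---|---|
| 0.20 | 1.673 | 16% | 1.00 |
| 0.25 | 1.604 | 20% | 0.96 |
| 0.30 | 1.538 | 23% | 0.92 |
| 0.40 | 1.418 | 29% | 0.85 |

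The true ratio is 1.00. If episodes and person-time both stop at A(d), the ratio is 1.00 in every row.

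For the yes/no endpoint, the recorded proportion is 1 − exp(−λL) + [λ·exp(−λL)/(λ + d)]·[1 − exp(−(λ + d)(T − L))]. With λ = 0.10:

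- True proportion: 1 − exp(−0.20) = 18.1% in both arms.
- Recorded: 14.1% at d = 0.30 and 15.3% at d = 0.20, a difference of −1.2 points.
- Standard error: √[(0.141×0.859 + 0.153×0.847)/925] = 1.65 points, so the expected z is −0.72.
- Chance of a nominally significant result favouring the arm that stops more: Φ(−1.96 + 0.72) = 10.8%, against 2.5%.

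For λ from 0.05 to 0.20 and d from 0.25 to 0.40 against 0.20, the difference runs from −0.3 to −4.0 points and that chance from 4.5% to 49%.

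**Step 4. Variations.**

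- With half of later transfusions captured, the full-follow-up ratio is 0.93 to 0.98. If those later episodes are counted but person-time is cut at EOT + 4 weeks, the ratio is 1.02 to 1.10, a bias the other way.
- With equal stopping there is no between-arm bias; only the levels are too low.
- Truncation can hide a real difference. If on-drug time is 60% against 70% of follow-up and the off-drug rate is twice the on-drug rate, the true ratio is (0.6 + 0.4×2)/(0.7 + 0.3×2) = 1.4/1.3 = 1.08. An on-drug comparison shows 1.00.

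**The case against.** A reader might infer that the protocol drops transfusion data once drug is stopped. It does not go that far. Transfusions are collected at EOT and 4 weeks later; note [dd], Protocol 11.5, Protocol 8.5.3 and SAP 2.2 all point to some later collection; and a list introduced as optimal need not be exhaustive. That answer stands against the strong reading. It does not remove the conflict: no section schedules transfusion questions between the Follow-up visit and EOS, and note [dd] alone could mean a single recall long after stopping.

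A reader might also infer that the SAP counts all off-drug time as transfusion-free. That follows for the yes/no endpoint, where no record becomes a no. For the rate, count and time-to-first endpoints it depends on undefined terms, and ending at-risk time at the last ascertainment is compatible with the wording. Nothing secures that reading either.

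Third, a reader might conclude that the plan favours vadadustat. The documents give no stopping rates, so no direction between the named arms is established.

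Two limits also stand. SAP 9.3 treats these endpoints as exploratory, without multiplicity control, and the narrow and broad-on-treatment rescue definitions (SAP 6.3.9) exclude therapy that starts after permanent discontinuation. The current protocol text available is the Colombia-specific Amendment 7, whereas the SAP covers both trials, so under-collection at all sites cannot be shown from it.

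**Conclusion.** The concern holds as a contradiction between passages combined with an analysis that does not guard against it. The documents must be reconciled on whether transfusions are collected after EOT + 4 weeks. Until then, transfusion frequency to EOS may be understated in both arms, and a between-arm comparison is biased towards the arm that stops drug more often if stopping differs. The size is illustrative only: a rate ratio of 0.85 to 0.96 for a true 1.00, assuming no later capture, stopping rates of 0.25 to 0.40 against 0.20 per year, equal transfusion hazards on and off drug, and all follow-up in the denominator. The consequence is confined to the RBC transfusion endpoints. The primary, key secondary, MACE and on-treatment rescue analyses are untouched.

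**What to change.** 1. Add RBC transfusions to the off-drug assessments in the Synopsis and Protocol 7.5.2, 7.5.5.4 and 9.3.12, consistent with note [dd] and SAP 2.2, so that they are asked at every contact already made through EOS. Align Protocol 11.5 with the result. This is the main repair: it serves all the transfusion endpoints and does not rely on stopping being unrelated to transfusion risk.
2. In SAP 6.3.7, D.2 and D.3, define at-risk follow-up, LN_FUT and the censoring date as the last contact at which transfusions were assessed, as the MACE SAP does for its outcomes. Apply the same cut-off to episodes and person-time.
3. In SAP D.1, add a version of the yes/no endpoint restricted to events up to EOT + 4 weeks, and report ascertained person-time by arm.

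The cost is one extra question per off-drug contact, some SAP wording, a derived date and some lost person-time. Truncated analyses may be informatively censored when subjects stop because the drug is not working, so they should be labelled supportive.

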3 LIST OF ABBREVIATIONS

AE	adverse event
ALT	alanine aminotransferase (SGPT)
ANOVA	analysis of variance
AST	aspartate aminotransferase (SGOT)
β-HCG	beta human chorionic gonadotropin
BCRP	breast cancer resistance protein
BUN	blood urea nitrogen
CBC	complete blood count
CHF	congestive heart failure
CIOMS	Council for International Organizations of Medical Sciences
CKD	chronic kidney disease
CKD-EPI	Chronic Kidney Disease Epidemiology Collaboration
CMH	Cochran-Mantel-Haenszel
CPK	creatinine phosphokinase
CRF	case report form
CRO	contract research organization
CRP	C-reactive protein
CS	clinically significant
CV	cardiovascular
CVD	cardiovascular disease
DD-CKD	dialysis-dependent chronic kidney disease
DILI	Drug-Induced Liver Injury
dL	deciliter
DNA	deoxyribonucleic acid
DVT	deep venous thrombosis
EAC	Endpoint Adjudication Committee
ECG	electrocardiogram
EDC	electronic data capture
eGFR	estimated glomerular filtration rate
EOS	end of study
EOT	end of treatment
EPO	erythropoietin
ESC	Executive Steering Committee
ESA	erythropoiesis-stimulating agent
ESRD	end-stage renal disease
EU	European Union
FDA	Food and Drug Administration
g	gram
GCP	Good Clinical Practice
GFR	glomerular filtration rate
GMP	Good Manufacturing Practice
HA	health authority
Hb	hemoglobin
HDL	high-density lipoprotein

HF	heart failure
HIF	hypoxia-inducible factor
HIFPH	hypoxia-inducible factor prolyl-hydroxylase
HIF-PHI	hypoxia-inducible factor prolyl-hydroxylase inhibitor
IC ₅₀	50% inhibitory concentration
ICH	International Conference on Harmonization
ID	identification
IDMC	Independent Data Monitoring Committee
IDMS	isotope dilution mass spectrometry
IEC	independent ethics committee
IMP	Investigational Medicinal Product
INR	international normalized ratio
IRB	institutional review board
IV	intravenous(ly)
IWR	interactive web response
JSDT	Japanese Society for Dialysis Therapy
JSN	Japanese Society of Nephrology
KDIGO	Kidney Disease: Improving Global Outcomes
kg	kilogram
LDH	lactate dehydrogenase
LDL	low-density lipoprotein
LLN	lower limit of normal
LTFU	Lost to Follow Up
MACE	major adverse cardiovascular events
MCH	mean corpuscular (cell) hemoglobin
MCHC	mean corpuscular (cell) hemoglobin concentration
MCV	mean corpuscular (cell) volume
MedDRA	Medical Dictionary for Regulatory Activities
MI	myocardial infarction
μM	micromolar
mg	milligram
mL	milliliter
mmhg	millimeters of mercury
mRNA	messenger ribonucleic acid
NDD-CKD	non-dialysis dependent chronic kidney disease
ng	nanogram
NYHA	New York Heart Association
PD	pharmacodynamics(s)
PE	pulmonary embolism
PHD	prolyl 4-hydroxylase domain
PI	package insert
PK	pharmacokinetic(s)
PP	per protocol
PT	prothrombin time
PTT	partial thromboplastin time
QA	quality assurance

QC	quality control
RBC	red blood cell
RDW	red cell distribution width
ROW	rest of world
SAE	serious adverse event
SAP	Statistical Analysis Plan
SC	subcutaneous(ly)
SCr	serum creatinine
SGOT	serum glutamic oxaloacetic transaminase (AST)
SGPT	serum glutamic pyruvic transaminase (ALT)
SmPC	summary of product characteristics
SV	Screening visit
TIBC	total iron binding capacity
TREAT	Trial to Reduce Cardiovascular Events with Aranesp Therapy
TSAT	transferrin saturation
uACR	urine albumin-to-creatinine ratio
ULN	upper limit of normal
US	United States
VEGF	vascular endothelial growth factor
VHP	Voluntary Harmonisation Procedures
WBC	white blood cell
WHO	World Health Organization

